4.1. Primary objectives

- 1) To assess the feasibility of uptake amongst people with 'high risk' or 'very high risk' type 2 diabetes.
- 2) To assess the usability of Fresh Start amongst people with 'high risk' or 'very high risk' type 2 diabetes.
- 3) To assess the acceptability of Fresh Start amongst people with 'high risk' or 'very high risk' type 2 diabetes.
- 4) To assess the acceptability of Fresh Start amongst HCPs.
- 5) To assess the cost-effectiveness of delivering Fresh Start.

4.2. Secondary objectives (Exploratory)

- 1) To assess the safety of Fresh Start.
- 2) To assess the impact of Fresh Start on clinical outcomes.

Imperial Clinical Trials Unit	SUB-STUDY SAP TEMPLATE – SUB-ANALYSES AND OBSERVATIONAL STUDIES	SOP_TEM_BS002
-------------------------------	---	---------------

5. Design

5.1. Study Design

An experimental feasibility study with an additional exploratory pre-test/post-test design using a matched control implemented via propensity score matching.

5.2. Treatment Groups

5.2.1. The *Fresh-Start* Service

This 12-week service has been designed to optimise patient care based on proactive identification and prioritisation of clinical risk based on health, socioeconomic and demographic factors.

Fresh Start seeks to assess whether alternative methods of healthcare delivery for people with high-risk or very high risk T2DM are safe, scalable, and cost-effective. Fresh Start has been co-designed with people with type 2 diabetes, healthcare professionals (GPs, specialists, nurses, podiatrists, dietitians) and commissioners from Collaboration Of North-West London Clinical Commissioning Groups (NWL CCGs).

The 12-week service comprises the following elements:

Proactive risk stratification. An electronic patient record (EPR) based risk stratification search is run at primary care practice level to identify T2DM patients at high risk of cardiovascular complications who may benefit from and be eligible for Fresh Start.

Video Group Consultations (VGC). Each patient is invited to attend a total of three VGCs during the 12-weeks lasting approximately one hour and 15 minutes each. Each session is facilitated by a Practice Nurse (PN) and consists of 6-10 people with T2DM. The self-reported Huma app (see below) and patient EPR data are used to populate a “Discussion Dashboard” which is used in each VGC to facilitate discussion. During the first VGC session, patient goals are discussed and adjusted in a group setting with topics relevant to their condition covered by the PN. Between each VGC session, patients spend time working on their goals and continuing to enter self-reported metrics into the Huma app. During the second and third VGC sessions, each patient is discussed, along with their performance against agreed goals. The PN also uses pre-prepared content to discuss topics relevant to managing type 2 diabetes (e.g., staying motivated, low carb diets).

Fresh Start educational email campaigns. Each patient is signed up to a series of educational email campaigns to complement the VGC sessions and provide broader education around type 2 diabetes management. Patients receive two emails per week during the 12-week service on a variety of topics.

Clinical protocols. A series of best-practice CRG approved clinical protocols are in place to be triggered based on thresholds and values captured via the Huma app and as part of the VGC sessions. Protocol examples include medications review, foot care, renal, and mental health.

Digital remote patient monitoring using blood pressure and blood sugar devices in combination with a smartphone application ('the Huma app'). Participants are provided with home monitoring devices and download the Huma app. Participants are shown how to use the devices, how to input measurements into a smart phone and how to set personal goals. Data recorded via the Huma app is self-reported and includes activity data, diet information, blood glucose measurements, blood pressure measurements, weight, and the Diabetes Distress Scale (a self-reported questionnaire used to measure distress related to living with diabetes). A Health Care Assistant (HCA) observes these data via a Huma clinician dashboard that complements the Huma app. The HCA presents these data in combination with relevant EPR data to the PN for review ahead of each VGC appointment.

One-to-one routine patient review. At the end of the 12-weeks participants are invited to a one-to-one review session with their primary care practice. The patient's progress over the 12-week service is reviewed and a decision is made whether to discharge patient, repeat them for another 12 weeks on Fresh Start, or escalate them to MDT.

5.2.2. Matched Control Group

Several of the study's objectives and associated outcome measures will require a control group for comparison. This includes the primary objective investigating cost-effectiveness and secondary objectives investigating safety and efficacy of Fresh Start on clinical outcomes.

To achieve this, the study will establish a matched control group using propensity score matching (PSM). PSM uses statistical techniques to construct an artificial control group by matching each study participant with a non-treated participant of similar characteristics. This is achieved by estimating the probability that a person would enrol in a program given a set of pre-defined characteristics, with the resulting probability providing a 'propensity score'.

Data for the matched control group will be identified using NWL's Whole of Systems Integrated Care (WSIC) database. WSIC links provider data from four acute, two mental health and two community Trusts across eight CCGs, social care data from eight boroughs and 380 GP practices to generate an integrated care record.

5.3. Study Population

The study population includes people with 'high risk' and 'very high risk' type 2 diabetes as defined by guidance for primary care from NHS England and NHS Improvement (London). All additional inclusion and exclusion criteria are defined within section 5.4 below:

5.4. Eligibility

5.4.1. Inclusion Criteria

- Patients over the age of 18 with the capacity to give consent
- Patients with 'high risk' OR 'very high risk' T2DM as defined by:
 - **Very high risk - T2DM with existing ASCVD** OR T2DM without ASCVD but with any **3 of the following**:
 - HbA1c >58 mmol/mol
 - SBP >140 mm Hg
 - Non-HDL >3.35 mmol/L or LDL-C >2.5 mmol/L
 - Nephropathy (eGFR <45 ml/min, or Urine ACR >3 mg/mol)
 - Retinopathy
 - Neuropathy (including moderate/high risk feet, previous foot ulceration and erectile dysfunction)
 - Currently smoking
 - **High risk - T2DM without ASCVD** but with any **2 of the following**:
 - HbA1c > 58 mmol/mol
 - SBP >140 mm Hg
 - Non-HDL >3.35 mmol/L or LDL-C >2.5 mmol/L
 - Nephropathy: eGFR <45 ml/min or Urine ACR >3 mg/mol
 - Retinopathy

5.4.2. Exclusion Criteria

- Participants too ill to participate in the study (i.e., presence of a life-threatening condition, expected survival less than 3 months, clinically unstable)
- Participants who have previously participated in efforts that have informed the design of this research.
- Participant without access to a smartphone.
- Non-English language (the remote monitoring technology currently does not support additional languages).
- Visual disability (the remote monitoring technology currently does not natively support visual assistance).
- Active severe mental illness (SMI).
- Alcohol / drug abuse.

Imperial Clinical Trials Unit	SUB-STUDY SAP TEMPLATE – SUB-ANALYSES AND OBSERVATIONAL STUDIES	SOP_TEM_BS002
-------------------------------	---	---------------

- Severe frailty (identified via the Electronic Frailty Index – eFI).
- Housebound / living in nursing home.
- Currently on the REWIND Programme (a NWL total diet replacement programme for patients with type 2 diabetes).

5.5. Sample Size

The study will seek to collect and analyse data from a minimum of 300 participants to Fresh Start. With an estimated enrolment rate of 20%, 1,500 eligible patients will need to be identified and we will be able to estimate this rate within a 95% confidence interval of +/-3%, accounting for variance inflation due to clustering with the assumption of 10 GP practices and Intraclass Correlation Coefficient (ICC) of 0.05.

The study's secondary objectives are exploratory only and will not be demonstrated to a level of statistical significance in this study.

5.6. Randomisation

No randomisation will take place during this feasibility study. Patients in the 'control' arm will be selected based on the Propensity Score Matching procedure described within section 7.1.2 .

Imperial Clinical Trials Unit	SUB-STUDY SAP TEMPLATE – SUB-ANALYSES AND OBSERVATIONAL STUDIES	SOP_TEM_BS002
-------------------------------	---	---------------

5.7. Schedule of Study Procedures

Step	Patient search	Outreach, Qualification & Booking	Onboard	Know Diabetes Emails	Huma App and Devices	Virtual Group Consultations (VGC)			12wk Review Discharge, Repeat or MDT
						Before	During	After	
Staff actions at primary care practice	Run EPR search report to find list of patients.	Contact patients by phone, invite them to the service and ensure they can participate.	Run virtual appointment or phone call to onboard patient onto the service.	Sign the patient up by email and make sure they are receiving emails OK.	Check Huma clinician dashboard daily for safety (red flags) and to see whether patients are using app.	Look at Huma dashboard, move some key data into EPR.	Run VGC session with 6-10 patients.	Internally discuss notes and actions from VGC after session.	Decide whether to discharge patient, repeat service for 12-weeks or escalate them to an MDT for further support.
		Book them onto a formal onboarding appointment and book bloods if missing.	Provide Huma app, book 3 x VGC sessions, sign up for Know Diabetes emails, answer questions	Patient collects devices from practice.	Escalate care if red flag spotted.	Fill out VGC “discussion board” slide and agree talking points for VGC session.	Review and discuss patient goals and clinical metrics.	Refer to clinical protocols; agree and action any required care plan and treatment changes or referrals.	
		Book to collect devices.			Patients set their own goals.	Discuss possible clinical and care plan decisions.	Identify and note clinical treatment or care plan changes and referrals required.		
How long it should take?	5m total	10m per patient	30m-45m per patient	1m per patient	1-2m per patient	1hr total	1hr15m total	1hr total	1hr total
How often it should be done?	Once, at beginning of 12 weeks	Once, at beginning of 12 weeks	Once, at beginning of 12 weeks	Twice, at beginning and at first VGC session	Daily	Before each VGC	During each VGC	After each VGC	Once, at end of 12 weeks

6. Variables of Analysis

6.1. Summary of Analysis Variables

Primary Objective	Outcome	Source	Freq.	Comp. w/ control?
1) To assess the feasibility of uptake amongst people with 'high risk' or 'very high risk' type 2 diabetes .	Patients offered Fresh Start vs. enrolled	EPR	Once	No
	Patients enrolled vs. downloading Huma app	Huma	Once	No
2) To assess the usability of Fresh Start amongst people with 'high risk' or 'very high risk' type 2 diabetes .	Number of VGCS attended	EPR	Every 4 weeks	No
	Number of Fresh Start emails opened	KD	Twice weekly	No
	Number of blood glucose measurements recorded	Huma	Daily	No
	Number of blood pressure measurements recorded	Huma	Daily	No
	Number of weight* measurements recorded	Huma	Daily	No
	Number of Diabetes Distress Scale measurements recorded	Huma	Monthly	No
3) To assess the acceptability of Fresh Start amongst people with 'high risk' or 'very high risk' type 2 diabetes .	Interviews with patients (x10)	Interview	At 12 weeks	No
4) To assess the acceptability of Fresh Start amongst HCPs .	Interviews with healthcare professionals (HCPs, x10)	Interview	After intervention	No
5) To assess the cost-effectiveness of delivering Fresh Start.	Number of primary care appointments per patient	EPR	Data extracted from EPR	Yes
	Cost per appointment per patient	EPR	Data extracted from EPR	Yes
	Cost of equipment per patient	Huma	N/A	No

* In the event where BMI data is more routinely collected the endpoint may be adjusted to BMI

Secondary Objective	Outcome	Source	Freq.	Compare with control?
1) To assess the safety of Fresh Start.	Number of deaths	EPR	Data extracted from EPR	Yes
	Number of emergency department admissions	WSIC	Data extracted from WSIC	Yes
	Number of hospital admissions	WSIC	Data extracted from WSIC	Yes
2) To assess the impact of Fresh Start on clinical outcomes .	HbA1c	EPR	Baseline, 12 weeks, 6 months	Yes
	Lipids, incl. LDL and non-HDL cholesterol	EPR	Baseline, 12 weeks, 6 months	Yes
	Weight *	EPR	Baseline, 12 weeks, 6 months	Yes
	Diabetes Distress Scale score (DDS[iii])	Huma	Monthly during service (and at 6 month follow-up appt.)	No
	Blood glucose time-in-range	Huma	Daily	Yes
	Systolic blood pressure (SBP)	Huma	Daily	Yes

* Note, if patient Height is also recorded BMI may be presented as an alternative

6.2. Primary Analysis Variables

6.2.1. Feasibility of uptake amongst people with ‘high risk’ or ‘very high risk’ type 2 diabetes

Feasibility of uptake is to be determined by the following measures:

- Patients enrolled with Fresh Start in comparison to those offered the Fresh Start service. Enrolment is defined as all patients entered within the study dataset. Offered is defined as those contacted about Fresh Start by their PCN by phone call or SMS and recorded in the Screening Log for that PCN.
- Patients collecting Fresh Start data in comparison to those enrolled. Patients collecting data is defined as a patient that records just one entry in any of the HUMA collected variables.

6.2.2. Usability of Fresh Start amongst people with ‘high risk’ or ‘very high risk’ type 2 diabetes.

Usability is to be determined by the following measures recorded over the 12-week assessment period:

- Number of **Video Group Consultations (VGC)** attended per patient
- Number of **Fresh Start** emails opened per patient
- Number of **Blood Glucose** measurements recorded per patient within HUMA
- Number of **Blood Pressure** measurements recorded per patient within HUMA
- Number of **Weight** measurements recorded per patient within HUMA
- Number of **Diabetes Distress Score (DDS)** measurements recorded per patient within HUMA

6.2.3. Acceptability of Fresh Start amongst people with ‘high risk’ or ‘very high risk’ type 2 diabetes.

Acceptability is to be determined by qualitative patient interviews completed by the ICHP team after the 12-week assessment period.

6.2.4. Acceptability of Fresh Start amongst HCPs

Acceptability is to be determined by qualitative interviews with HCPs completed by the ICHP team after the Fresh Start intervention has been delivered to enrolled patients

6.2.5. Cost-effectiveness of delivering Fresh Start

Cost-effectiveness is to be determined by the following measures:

- Number of primary care appointments per patient - as entered in study dataset over the 12-week assessment period
- Cost per appointment per patient - as entered in study dataset
- Cost of equipment per patient – defined below:

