7.1.2. Propensity Score Matching

For the primary cost-benefit comparison and secondary safety and efficacy comparisons, study data will be compared against a matched-control group established via propensity score matching. This is achieved by deriving a propensity score for each enrolled patient based on the following characteristics:

- Age
- Gender
- Geographical proximity
- Social deprivation index (by practice)

- Ethnicity

Using the above categories, taking 'arm' as the dependent variable, logistic regression using a generalised logit model will be used to generate the estimated propensity scores. Scores are also applied to a control 'arm' taken from the WSIC database as section 5.2.2 with everyone in the matched control identified within one month of the index case. The scores are then used to 'pair-up' patients within both groups, patients will be matched on a 1:1 basis without replacement.

Scores are to be calculated using PSOCORE in STATA. Matching is to be carried out using PSMATCH2 (or a suitable alternative). Balancing on matching variables is to be checked once matching is completed using PSTEST. If any variable is found to be unbalanced the matching is repeated, either adjusting the matching method or caliper used.

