7.5.5. Cost-effectiveness of delivering Fresh Start

From the three sets of data established in 6.2.6, cost-effectiveness of Fresh Start is to be assessed via the following:

- Number of primary care appointments per patient - as entered in study dataset over the 12-week assessment period

Summary statistics will be derived for mean, sd, median, 1st/3rd quartiles, and minimum/maximum. Results will be presented as mean (SD) for normally distributed data and median [Q1-Q3] for skewed.

To assess for differences in frequency of appointments per patient between Fresh Start and the matched control group, a Poisson-based mixed effects model with covariates for sex, age, social deprivation index will be used allowing for clustering by GP practice.

- Cost per appointment per patient - as entered in study dataset

Summary statistics will be derived for mean, sd, median, 1st/3rd quartiles, and minimum/maximum. Results will be presented as mean (SD) for normally distributed data and median [Q1-Q3] for skewed.

To assess for differences in cost of appointments per patient between Fresh Start and the matched control group, a mixed-model approach with covariates for sex, age, social deprivation index will be used allowing for clustering by GP practice.

- Cost of equipment per patient

Imperial Clinical Trials Unit	SUB-STUDY SAP TEMPLATE – SUB-ANALYSES AND OBSERVATIONAL STUDIES	SOP_TEM_BS002
-------------------------------	---	---------------

Costs per patient will be estimated using the figures provided in section 6.2.6.1. Once established, summary statistics will be derived for mean, sd, median, 1st/3rd quartiles, and minimum/maximum. Results will be presented as mean (SD) for normally distributed data and median [Q1-Q3] for skewed

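### The primary cost-effectiveness objective has no effect measure and no total cost per patient, so the plan supports only a partial cost comparison

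*SAP*

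**What the plan says.** Cost-effectiveness is a primary objective in protocol section 2 and in SAP 4.1 ("To assess the cost-effectiveness of delivering Fresh Start"). SAP 6.2.5 gives its content: "Cost-effectiveness is to be determined by the following measures", followed by three entries:

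- First, a count of resource use: "Number of primary care appointments per patient - as entered in study dataset over the 12-week assessment period"
- Second, a price attached to that resource: "Cost per appointment per patient - as entered in study dataset"
- Third, the devices, priced from the list in SAP 6.2.6: "Cost of equipment per patient – defined below"

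The outcome tables in protocol 3.6, SAP 6.1 and SAP 7.2 list the same three. The first two are marked for comparison with the matched control and equipment is not.

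SAP 7.5.5 is the whole analysis method. It plans a Poisson mixed model for the number of appointments, a mixed model for appointment cost, and a summary only for equipment. For each measure it states "Summary statistics will be derived for mean, sd, median, 1st/3rd quartiles, and minimum/maximum", and then gives a rule on which of these to show: "Results will be presented as mean (SD) for normally distributed data and median [Q1-Q3] for skewed".

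SAP 7.1.2 gives the same analysis another name when it introduces the matching: "For the primary cost-benefit comparison and secondary safety and efficacy comparisons". Appointments are counted over 12 weeks in SAP 6.2.5 and 7.5.5, but up to 6 months after enrolment in the SAP 7.2 summary table.

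**The concern.** A cost-effectiveness statement needs a difference in cost and a difference in effect, brought together in some way. Here neither half is complete. No effect enters the objective, and the cost half is left in separate pieces.

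The protocol says the results may support continuing the service, and the label that cost-effectiveness carries is primary, not exploratory. Read on this objective alone, a service that costs more and improves HbA1c would look worse than one that costs less and does not. A report that follows the plan exactly and then concludes on cost-effectiveness would state something the analysis does not contain.

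The presentation rule adds a smaller difficulty. A median cost cannot be multiplied up to a total or set beside a mean effect, yet it is the figure to be put forward when costs are skewed.

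**Working it through.** The documents give no cost-effectiveness figure to reproduce. The check is a reading of the sections, plus arithmetic on the unit costs in SAP 6.2.6.

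**1. Is there an effect measure?** Of the three measures in SAP 6.2.5, three are resource or cost items and none is a health effect. SAP 7.5.5 names no ratio, net benefit, threshold or cost-consequence display. Between-group differences in HbA1c, lipids, weight and a composite safety outcome are planned in SAP 7.6 against the same matched control, but nothing joins them to cost.

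**2. Is there a total cost per patient?** The quantity needed for each patient is

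cost = (number of appointments × cost per appointment) + equipment (Fresh Start arm only).

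No section defines it.

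- Separate summaries of count N and unit cost C do not supply the first term, because mean(N × C) = mean(N) × mean(C) + cov(N, C). The product of the two means is right only if the covariance is zero.
- The modelled outcome in SAP 7.5.5 is headed as cost per appointment but described in the model sentence as cost of appointments per patient. If the second is meant, the model does give an appointment-cost difference, still without equipment.
- Training (protocol 3.8) and daily dashboard review (SAP 5.7) are outside the three measures.

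**3. Size of the equipment omission.** Inputs are the SAP 6.2.6 unit costs (no currency printed). Assumption: one unit of each item and one of the two blood pressure monitors per patient.

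- Common items: 2.00 + 5.95 + 3.77 + 3.00 + 20.00 = 34.72
- With the cheaper monitor: 34.72 + 37.93 = 72.65
- With the dearer monitor: 34.72 + 130.00 = 164.72
- For 300 participants (SAP 5.5): 300 × 72.65 = 21,795, or 300 × 164.72 = 49,416

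**4. Mean against median on the same prices.** Let s be the share of patients given the dearer monitor (assumed; the documents do not state it). Mean = 72.65 + 92.07 × s.

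| s | Mean | Median | Median relative to mean |
|---|---|---|---|
| 10% | 81.86 | 72.65 | 11% lower |
| 40% | 109.48 | 72.65 | 34% lower |
| 80% | 146.31 | 164.72 | 13% higher |

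The two can differ materially, and the direction is not fixed.

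**5. Is the mean withheld?** No. SAP 7.5.5 derives it without a condition on skewness. SAP Appendix 1 assigns cost per appointment to Templates 3 and 5 and equipment to Template 3. Template 3 has a mean column, and Template 5 shows coefficients with 95% CIs. The difficulty is limited to which figure the text of 7.5.5 says to present.

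**The case against.** The best defence is that this is a feasibility study whose clinical effects are declared exploratory, and the protocol says a larger and longer study would be needed. Declining to form a ratio from such effects is sensible. Costs and consequences will both be reported against the same matched control, so a reader could set them side by side. This stands as an argument against a ratio. It does not justify the label, because the exploratory caveat covers the secondary objectives and cost-effectiveness is primary. It also does not supply the missing total cost.

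On medians, the defence largely succeeds. A reader might infer that the median rule by itself rules out any budget conclusion. The documents do not support that: the mean is always derived, the table shell prints it, and a between-group model of appointment cost is planned. If that model is linear on untransformed cost, its coefficient is an adjusted mean difference with an interval.

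A reader might also put a figure on a budget shortfall. For log-normal costs, median/mean = 1/√(1 + CV²), which is 0.707 at CV 1 and 0.555 at CV 1.5, or 29% and 45% below the mean. That is an assumed shape with assumed CVs. The documents give no cost distribution and set no budget-impact objective, so these figures say nothing about this plan.

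**Conclusion.** The concern holds as a point about what the objective can conclude. None of the three measures is an effect, no step links cost to outcome, and no total or incremental cost per patient is defined. The plan therefore supports a partial cost comparison, and neither the cost-effectiveness label nor the cost-benefit label is earned. This rests on the text alone.

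The equipment left out of the between-group comparison is 72.65 to 164.72 per Fresh Start patient, assuming one unit of each item and one monitor. More strips or lancets per patient would raise it.

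The median rule is a secondary fault of presentation: it puts forward the wrong headline figure but does not remove the right one.

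**What to change.** **1. Define the cost.** In SAP 6.2.5, define one cost per patient: appointments times their cost, plus equipment in the Fresh Start arm. State the equipment quantities assumed. Use one window, reconciling the 12 weeks in 6.2.5 and 7.5.5 with the 6 months in 7.2.

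**2. Then choose one of two routes.**

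- Relabel the objective and its conclusion a partial cost comparison. The protocol carries the same objective in sections 2, 3.5 and 3.6, so the wording there needs to match.
- Or add one cost-consequence table on the same matched sample. It would show the mean cost difference with 95% CI beside the between-group HbA1c and composite safety differences of SAP 7.6, with no ratio formed. The windows of the table's columns should be stated.

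In either case, align the term used in SAP 7.1.2.

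**3. Make the mean the headline.** In SAP 7.5.5, present the arithmetic mean cost and the mean difference with 95% CI whatever the skewness, with the median and quartiles as supplementary. The mean is already produced, so this only removes the rule that would present the median instead.

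**4. Choose the interval with care.** It should respect the 1:1 matching and the clustering by practice. A simple bootstrap of practices is not suitable: about 10 intervention practices are assumed (SAP 5.5), and controls come from a database of 380 practices, so resampling practices would not in general keep matched pairs together.

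**Cost.** SAP wording, a matching protocol edit if the objective is renamed, and at most one table. No new data are needed. The downside is wide, exploratory intervals in the added table, or a less ambitious label. Training and dashboard time stay outside the total, so it should still be called partial.

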It is our opinion that generating credible evidence for digital health solutions remains an industry-wide challenge, hindering widespread adoption, and that traditional approaches present limitations for researchers to create evidence. Evaluation of digital health solutions has also been identified as requiring improvement and has been cited as a major obstacle for wider adoption.^{7 8} This study will use pragmatic methods to evaluate Fresh Start, with a view to support successful adoption of Fresh Start in primary care practices in the UK.

2. Study aims and objectives

The aim of T2DEx is to assess the feasibility, usability, acceptability, cost-effectiveness and safety of a remote care service (“Fresh Start”) in primary care for people with ‘high risk’ or ‘very high risk’ Type 2 Diabetes in North West London.

The study will assess patient and clinician experience metrics, the feasibility of implementation including uptake and patient/physician acceptability for data collection procedures, and the resources needed to manage and implement Fresh Start. The study will also assess the impact of Fresh Start on clinical outcome measures (e.g., HbA1c, risk factor control, time at goal).

The results of this may support continuation of Fresh Start. A follow-up study with a larger number of participants and longer duration would be required to assess a statistically significant impact on secondary objectives.

Primary objectives:

1. To assess the **feasibility of uptake** amongst people with 'high risk' or 'very high risk' type 2 diabetes.
2. To assess the **usability** of Fresh Start amongst **people with 'high risk' or 'very high risk' type 2 diabetes**.
3. To assess the **usability** of Fresh Start amongst **HCPs**.
4. To assess the **acceptability** of Fresh Start amongst **people with 'high risk' or 'very high risk' type 2 diabetes**.
5. To assess the **acceptability** of Fresh Start amongst **HCPs**.
6. To assess the **cost-effectiveness** of delivering Fresh Start.

Secondary objectives (**EXPLORATORY** only and will not be demonstrated to a level of statistical significance):

1. To assess the **safety** of **Fresh Start**.
2. To assess the **impact of Fresh Start on clinical outcomes**.

3. Study design and methods

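### The primary cost-effectiveness objective has no cost measure for Fresh Start staff time outside appointments, about 2.2 to 4.0 hours per patient on the plan's own times

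*SAP*

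**What the plan says.** Cost-effectiveness of delivering Fresh Start is a primary objective in both documents. SAP 6.2.5 opens with "Cost-effectiveness is to be determined by the following measures" and gives three. The first is "Number of primary care appointments per patient - as entered in study dataset over the 12-week assessment period". The second is what each appointment costs, again taken from the dataset, and the third is what the equipment costs.

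SAP 7.5.5 says that "cost-effectiveness of Fresh Start is to be assessed via the following" and repeats the same three. For the third it says "Costs per patient will be estimated using the figures provided in section 6.2.6.1"; the price list itself stands at 6.2.6 and holds seven devices and consumables, with no staff or software line. Protocol 3.6, SAP 6.1 and SAP 7.2 agree with this list. They mark the two appointment measures for comparison with control and equipment as not compared.

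Protocol section 2 names, among the things the study will assess, experience, feasibility of implementation, "and the resources needed to manage and implement Fresh Start". SAP 5.7 and Protocol Appendix 2 give a duration and a frequency for every delivery task. One of these is "Check Huma clinician dashboard daily for safety (red flags) and to see whether patients are using app", at 1 to 2 minutes per patient. Others are a 10-minute outreach call, and one hour of work before and one hour after each VGC.

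**The concern.** Part of what it takes to deliver Fresh Start is done when no patient is being seen: calling people on the search list, reading the dashboard, moving app data into the record, filling in the discussion board, and agreeing actions after a session. The plan knows how long these tasks should take, but no outcome collects, values or analyses that time. Matched controls have none of these tasks, so leaving them out lowers the recorded cost of Fresh Start and of nothing else.

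At stake is a primary objective whose result may be used to support continuing the service. A commissioner who reads a cost per patient built from appointments and devices would not see a workload that practices have to staff. The stated aim of assessing the resources needed would be met only in part: appointments and equipment are resource measures, but the monitoring and preparation work is missing.

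**Working it through.** The documents give no total for staff time, so there is no plan figure to reproduce. The total below is built from SAP 5.7, counting only work with no patient contact beyond the outreach call.

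**Inputs.** The service lasts 12 weeks = 84 days (SAP 5.2.1). There are three VGCs of 6 to 10 patients (SAP 5.2.1, 5.7). Task times are from SAP 5.7. The one hour before and one hour after a VGC are read as per session, shared by the group. One staff member per task is assumed.

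| Task | Formula | Minutes per patient |
|---|---|---|
| Outreach call | 1 × 10 | 10 |
| Dashboard check | 84 × 1 to 84 × 2 | 84 to 168 |
| VGC preparation and debrief | 3 × (60 + 60) / 10 to 3 × (60 + 60) / 6 | 36 to 60 |
| **Total** | | **130 to 238** |

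130 / 60 = 2.17 h and 238 / 60 = 3.97 h, so about 2.2 to 4.0 h per patient. For 300 participants: 300 × 130 / 60 = 650 h to 300 × 238 / 60 = 1,190 h.

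Email sign-up (1 minute, twice) is left out. Protocol 3.7 places it inside the onboarding call and the first VGC, so counting it would risk charging it twice.

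**Sensitivity.**

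- Dashboard checks on weekdays only (assumption; the documents say daily), 12 × 5 = 60 checks: 10 + 60 + 36 = 106 to 10 + 120 + 60 = 190 minutes, or 1.8 to 3.2 h.
- No dashboard time at all: 46 to 70 minutes, or 0.8 to 1.2 h. The dashboard is therefore 65% (84/130) to 71% (168/238) of the total.
- Outreach to people who do not enrol: at the planned 20% enrolment there are four per enrolee, so at most 4 × 10 = 40 minutes more, giving 170 to 278 minutes (2.8 to 4.6 h). This is an upper figure, because SAP 6.2.1 allows contact by SMS.
- If onboarding (30 to 45 minutes) and the VGC sessions (3 × 75 = 225 minutes, divided by 10 or 6 = 22.5 to 37.5) were not logged as appointments either: 182.5 to 320.5 minutes, or 3.0 to 5.3 h with one staff member.

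**In money.** The documents give no staff rate. At an assumed 15 to 30 GBP per hour, 130/60 × 15 = 32.50 and 238/60 × 30 = 119.00, so roughly 33 to 120 GBP per patient. With weekday checks: 106/60 × 15 = 26.50 to 190/60 × 30 = 95.00.

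**Against what is counted.** One of each item in SAP 6.2.6, with either blood pressure monitor (the list names no currency; GBP is assumed):

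- 37.93 + 2.00 + 5.95 + 3.77 + 3.00 + 20.00 = 72.65
- 130.00 + 2.00 + 5.95 + 3.77 + 3.00 + 20.00 = 164.72

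The uncosted time is of the same order as the equipment cost.

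**The case against.** A reader might infer more: that the comparison is bound to favour Fresh Start. The documents do not support that, for three reasons.

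First, the SAP does not say whether onboarding, the three VGCs and the 12-week review are primary care appointments. If they are, each Fresh Start patient carries up to 1 + 3 + 1 = 5 contacts that the service itself creates, and both appointment models would tend to count against it. Nor does the SAP say whether a VGC is costed once per group or at a full unit cost for each attendee; the second would overcharge a session shared by 6 to 10 people.

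Second, the plan never forms a total cost for the Fresh Start arm. Equipment is summarised for that arm alone, and the two appointment measures are analysed separately. No net saving is calculated from which the missing time could be said to have been dropped.

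Third, neither document describes how control patients receive care or what the unit cost of an appointment contains. That usual care is fully captured by appointments, or that Fresh Start moves work out of appointments, is inference. The unit cost could also include some overhead, although nothing says so.

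The size is also open to challenge. The dashboard dominates it, and the upper figures suppose that every enrolee is checked every day for 84 days, whereas SAP 7.4 and 7.7 expect some who do not use the app or do not adhere. This is a fair point, and it is why the weekday and no-dashboard figures are shown.

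What stands after all this is the gap itself: these tasks have no cost line, and the sign of that one missing item is known.

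**Conclusion.** The concern holds as an incomplete cost measure in a primary objective. Followed as written, the plan would understate the cost of delivering Fresh Start by about 2.2 to 4.0 staff hours per patient on planned times, or 1.8 to 3.2 hours with weekday dashboard checks. At the assumed rates the first range is roughly 33 to 120 GBP.

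This rests on the SAP 5.7 times being realistic, groups of 6 to 10 with full attendance (smaller groups raise the figure), one staff member per task, and the assumed hourly rates. It does not show that the overall comparison with control is biased towards the service; that stays open until the SAP defines which Fresh Start contacts are appointments and how a VGC is costed. The change is worth making because most of the inputs are already tabulated.

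**What to change.** Add to SAP 6.2.5 and 7.5.5 a fourth measure: non-appointment delivery time and cost per Fresh Start patient.

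- **Build** it from the SAP 5.7 times, each patient's days on the service, and VGC group size from attendance records, multiplied by a stated unit cost for the staff grade that does each task. Use the same time window as the appointment measure.
- **Outreach:** include people who were phoned but did not enrol, from the Screening Log, and not those contacted only by SMS. If the log does not separate the two, show the range from none to all phoned.
- **Sensitivity:** report over the stated time ranges and over daily against weekday dashboard checks.
- **Reporting:** place it beside equipment cost. Give the between-group difference in appointment cost twice, without and with equipment and delivery time added to the Fresh Start arm.
- **Counting rule:** state whether onboarding, VGCs and the 12-week review are appointments, count each contact once, and divide shared VGC time by group size.
- **Exclusions:** state that training and app or platform costs lie outside this measure.

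The cost is SAP wording, a small calculation, and sourcing of staff unit costs, which are not among the listed variables; days on the service and group size must also be derived. The Fresh Start cost becomes less favourable and rests partly on planned rather than observed times. If the measure is not added, the least change is to relabel the outcome as appointment and equipment costs.
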